7.9. Adverse Events of Special Interest

An AESI is an AE (serious or nonserious) of scientific and medical concern specific to study drug, for which ongoing monitoring and immediate notification by the Investigator to the Sponsor is required. Such AEs may require further investigation to characterize and understand them. Adverse events of special interest may be added or removed during a study by a protocol amendment.

The following AEs are considered AESIs:

- SCC
- Actinic keratosis
- Keratoacanthoma

7.10. Adverse Event Reporting Periods

The AE (including SAEs and AESIs) reporting period begins from the time that the patient provides informed consent through and including 30 days after the last administration of the study drug for all randomized patients. Patients who are not randomized will have AEs collected until the time of screen failure. Any SAE or AESI occurring after the reporting period must be promptly reported if a causal relationship to study drug is suspected.

If a patient begins a new anticancer therapy, the safety reporting period ends at the time the new treatment is started; however, death must always be reported when it occurs during the safety reporting period irrespective of intervening treatment.

7.11. Adverse Event, Serious Adverse Event, and Adverse Event of Special Interest Reporting Requirements

Each patient must be carefully monitored for the development of any AEs. This information must be obtained in the form of non-leading questions (eg, “How are you feeling?”) and from signs and symptoms detected during each examination, observations of study personnel, and spontaneous reports from patients.

All AEs (serious and non-serious) spontaneously reported by the patient and/or in response to an open question from study personnel or revealed by observation, physical examination or other diagnostic procedures must be recorded. When possible, signs and symptoms indicating a common underlying pathology must be noted as 1 comprehensive event. Accompanying signs or symptoms (eg, abnormal laboratory values) must not be reported as additional AEs. If a diagnosis is unknown, one or more symptoms may be reported as separate AEs. If an underlying diagnosis is subsequently determined for the reported symptom(s), then the reported symptom(s) term(s) must be revised to be “attributed” or “due” to the diagnosis.

All SAEs and AESIs that occur within the reporting period, regardless of causality, must be reported by the Investigator to WCT PVG **within 24 hours** from the point in time when the Investigator becomes aware of the SAE or AESI. SAEs and AESIs must be followed until resolution, the condition stabilizes, or the Investigator and Sponsor agree that follow up is not required. For the purposes of study analysis, if the event has not resolved at the end of the study reporting period, it must be documented as ongoing. For purposes of regulatory safety monitoring, the Investigator is required to follow the event to resolution and report to the Sponsor the outcome of the event. Further instructions on reporting of SAEs will be provided in the Study Reference Manual.

If there are serious, unexpected, suspected adverse drug reactions (SUSARs) associated with the use of the study drug, the Sponsor or authorized designee will ensure that the appropriate regulatory agency(ies) and all participating investigators are notified on an expedited basis. In addition, the Sponsor or authorized designee will be responsible for notification of SUSARs to the ethics committee. It is the responsibility of the Investigator to promptly notify the local IRB/IEC/REB of SUSARs according to the institutional policy. An unexpected event is one that is not reported in the IB.

7.12. Abuse, Misuse, Overdose, and Medication Error

Occurrences of events of overdose, drug misuse, drug abuse and medication error must be reported to the Sponsor.

Abuse of a medicinal product: Persistent or sporadic, intentional excessive use of medicinal products, which is accompanied by harmful physical or psychological effects [DIR 2001/83/EC Art 1(16)].

Misuse: Intentional and inappropriate use of a medicinal product not in accordance with the prescribed or authorized dose, route of administration, and/or the indication(s) or not within the legal status of its supply.

Overdose: Administration of a quantity of study drug given per administration or per day, which is above the assigned dose.

Medication Error: An error made in prescribing, dispensing, administration, and/or use of the study drug. Medication errors are reportable to the Sponsor as defined below.

- The dispensing, administration and/or use of the unassigned study drug.
- The administration and/or use of an expired study drug.

Note: Cases of patients missing doses of the study drug are not considered reportable as medication errors.

AEs or SAEs associated with drug abuse, misuse, overdose, or medication error must be reported as appropriate ([Section 7.1](#) and [Section 7.8](#)).

8. WITHDRAWAL AND REPLACEMENT OF PATIENTS

8.1. Withdrawal of Patients

A patient is free to withdraw from the study drug and/or study for any reason and at any time without giving reason for doing so and without penalty or prejudice. The Investigator is also free to terminate a patient's involvement in the study at any time if the patient's clinical condition warrants it. The primary reason for discontinuation or withdrawal of a patient from the study must be determined using the following categories:

- Adverse event
- Death
- Lost to follow-up
- Non-compliance with study drug
- Physician decision
- Pregnancy
- Confirmed progressive disease by Investigator assessment
- Confirmed progressive disease by independent radiologic review
- Protocol deviation
- Termination of site by Sponsor
- Termination of study by Sponsor
- Withdrawal by patient
- Any other reason that in the opinion of the Investigator, would justify removing the patient from the study, based on the best interest of the patient

If a patient voluntarily withdraws from the study, the Investigator should attempt to contact the patient to determine the reason(s) for discontinuation and request the patient return for an EOT Visit and Safety Follow up Visit. If a patient withdraws from the study for any reason other than withdrawal by the patient, an EOT Visit and Safety Follow up Visit must be conducted, and the patient must be followed for overall survival. . Patients must return all used, partially used, and unused study drug bottles.

8.2. Replacement of Patients

Patients will not be replaced in this study.

9. STATISTICAL CONSIDERATIONS

9.1. Determination of Sample Size

The sample size selection of approximately 120 patients (n=80 DCC-2618, n=40 placebo) was based on considerations for powering of the primary endpoint, key secondary endpoint, detection of rare safety events and overall exposure to DCC-2618, and assuming 15% patient dropout. Patients will be randomized in a 2:1 ratio of DCC-2618 versus placebo.

This sample size [105 patients (n=70 DCC-2618, n=35 placebo) with 90 events (55 DCC-2618, 35 placebo) at the final analysis] will have at least 90% power to detect a difference in PFS between DCC-2618 and placebo assuming a median PFS of 4.5 months for DCC-2618 and 1 month for placebo. Moreover, this assumes 9 months of uniform recruitment and 6 additional months of follow-up (total patient follow-up of 15 months).

Furthermore, 105 patients (n=70 DCC-2618, n=35 placebo) will have approximately 80% power to detect a 0.2 difference in ORR assuming that the ORR for DCC-2618 = 0.22 and the ORR for placebo = 0.02.

In addition, a minimum sample size of 80 DCC-2618 patients allows adequate power to detect the incidence of rare safety events. A sample of 80 patients yields 95% probability that the study will reveal at least one occurrence of all safety events that occur in patients at a rate of 4.0% or greater. This in combination with the exposure to DCC-2618 from other studies conducted in this clinical program will meet the recommendations for overall exposure recommended by FDA.

9.2. Analysis Endpoints

9.2.1. Primary Endpoint

9.2.1.1. Efficacy

Progression-free survival based on independent radiologic review using modified RECIST (1; [Appendix 17.1](#)). Modified RECIST criteria includes:

- No lymph nodes chosen as target lesions; enlarged lymph nodes followed as non-target lesions;
- No bone lesions chosen as target lesions;
- PET not acceptable for radiological evaluation;
- A progressively growing new tumor nodule within a pre-existing tumor mass must meet the following criteria to be considered as unequivocal evidence of progression according to the modification of RECIST Version 1.1: (a) the lesion is at least 2 cm in size and definitively a new active GIST lesion (eg, enhancing with contrast or other criteria to rule out artefact); or (b) the lesion has to be expanding on at least 2 sequential imaging studies.

9.2.2. Secondary Endpoints

9.2.2.1. Key Secondary Endpoints

9.2.2.1.1. Efficacy

- ORR based on independent radiologic review

9.2.2.2. Additional Secondary Endpoints

9.2.2.2.1. Efficacy

- TTP based on independent radiologic review
- OS
- Time to best response
- PFS based on Investigator assessment
- QOL as determined by changes from baseline in EORTC-QLQ-C30 and EQ-5D-5L
- Disease control rate (DCR; CR + PR + SD) at 12 weeks

9.2.2.2.2. Safety

Safety endpoints that will be evaluated include TEAEs, AESIs, SAEs, dose reduction or discontinuation of study drug due to toxicity; and changes from baseline in ECOG PS, vital signs, ECG, LVEF, dermatologic examinations, and clinical laboratory parameters.

9.2.2.2.3. Pharmacokinetics

- Correlation of PK with efficacy/safety
- Population PK

9.2.3. Exploratory Endpoints

9.2.3.1. Efficacy

- PFS by Investigator assessment after dose escalation to DCC-2618 150 mg BID

9.2.3.2. Biomarkers and Pharmacodynamics

- Type and burden of mutations in plasma cfDNA
- Treatment effect of DCC-2618 on cfDNA mutation allele frequency
- Potential TKI-resistance mechanisms of GIST at time of progression
- Concordance between KIT, PDGFRA and other gene mutations in tumor and cfDNA

9.2.3.3. Healthcare Utilization

- Changes over time in healthcare utilization

9.3. Populations for Analysis

The following populations will be used in the analysis: Intent-to-treat (ITT), Safety, PK, and Per Protocol (PP).

The ITT population is defined as all patients who signed the informed consent and were randomized. The ITT population will be used for all efficacy analysis as a primary analysis set with treatment assignment based on randomization.

The Safety population is defined as all patients who have received at least 1 dose of study drug. The Safety population will be used for all safety analysis with treatment actually received.

The PK population will include all randomized subjects who received at least 1 dose of DCC-2618 and had at least 1 non-missing PK concentration in plasma reported for DCC-2618 or DP-5439.

A PP population may be included if there are patients in the ITT population who do not have protocol violations that are expected to compromise the efficacy and/or safety assessments (eg, patients enrolled who do not meet key eligibility criteria) during the study. Protocol violators resulting in exclusion from the PP population will be identified and documented prior to database lock.

9.4. Procedures for Handling Missing, Unused, and Spurious Data

All available data will be included in data listings.

Algorithms for imputing partial or missing dates are shown in Table 17. If a period determination cannot be made for an adverse event, it will be attributed to the randomized blinded period, with missing dates imputed as explained in Table 18. Adverse event end dates are imputed to facilitate calculation of AE duration.

Table 17: Partial or Missing Date Algorithms

Variable	Missing Day	Missing Day, Month	Missing Day, Month, Year
Date of Last Therapy/Date of Initial Diagnosis	Assign 1	Assign January 1 if prior to date of informed consent, otherwise use date of informed consent	Missing (do not impute)
Adverse Event/Start Date	Assign first day of month unless it is the year/month of first dose of study medication. Otherwise, assign date of first dose of study medication or AE end date (if not missing) whichever is earlier.	Assign January 1 unless the year is year of first dose of study medication Otherwise, assign date of first dose of study medication or AE end date (if not missing) whichever is earlier.	Assign date first dose of study medication.
Adverse Event End Date	Assign the last day of the month or end of study date, whichever is earlier.	Assign December 31 or end of study date, whichever is earlier.	If ongoing, end date is missing. Otherwise, assign end of study date.

Table 18: Imputation Rules for Questionnaires

Questionnaire	Number of items missing < half	Number of items missing > half
EORTC-QLQ-C30	No imputation for missing	Impute missing values by using the average score from the patients with non-missing values from within the same randomization strata

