5.9. Method of Assigning Patients to Treatment

Patients will be randomized in a 2:1 ratio to DCC-2618 150 mg or placebo. Randomization will be stratified by:

- Patients who have received 3 prior anticancer treatments versus patients who have received ≥ 4 prior anticancer treatments
 - It should be noted that enrollment for patients who have received ≥ 4 prior anticancer treatments will be limited to 40% of the overall sample size.
 - Prior anticancer treatments are only counted once and without regard to when the patient received treatment, unless they were given as combination treatments.
- ECOG=0 versus ECOG=1 or 2

The IRT will be used to assign study drug treatment. Detailed instructions for randomization will be provided separately.

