6.10.3. Patient Reported Outcome Measurements

6.10.3.1. European Organisation for Research and Treatment of Cancer Quality of Life Questionnaire for Cancer 30-item (EORTC QLQ-C30)

The EORTC QLQ-C30 is a validated, standardized, patient-completed questionnaire used extensively in international clinical studies and developed to assess health-related quality of life in patients with cancer (28). The time required for completion is approximately 3-5 minutes. Validated translations will be provided for sites in non-English-speaking countries.

The questionnaire is composed of multi-item and single-item scales. These include 5 functional scales (physical functioning, role functioning, emotional functioning, social functioning, cognitive functioning), 9 symptom scales (fatigue, nausea and vomiting, pain, dyspnea, insomnia, appetite loss, constipation, diarrhea, and financial difficulties), and a global health status/quality of life (QOL) scale.

The functioning and symptoms scales ask the patient to rate his or her experience for a particular item during the last week by selecting Likert scale response options of “not at all,” “a little,” “quite a bit,” or “very much.” The 2 items comprising the global health status scale also evaluate the patient’s experience over the past week using numerical rating scales with 1 representing “very poor” and 7 representing “excellent.”

Patients will be asked to complete EORTC-QLQ-C30 in their native language using an electronic patient reported outcome (ePRO) system on provided tablet computers before dosing at the visits indicated in [Table 1](#) (schedule of assessments) and [Table 2](#) (schedule of assessments for crossover).

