9.8.5. Efficacy Analysis

9.8.5.1. Primary Endpoint: Progression-free Survival Analysis

The primary endpoint of PFS (reported in weeks) is defined as the interval between the date of randomization and the earliest documented evidence of disease progression based on the independent radiologic review, or death due to any cause. Patients who undergo surgical resection of target or non-target lesions, who have received other anticancer treatments, or patients who do not have a documented date of progression or death due to any cause will be censored at the date of the last assessment. Analysis for PFS will be stratified by the randomization stratification factors [prior lines of therapy (3 versus ≥ 4) and ECOG (0 versus 1 or 2)]. The p-value will be from a 2-sided stratified Log-rank test at 0.05 significant level for evaluation of treatment difference. Point estimate of hazard ratio will be obtained from a

Cox regression model with the treatment and the randomization stratification factors as fixed factors and its 95% CI will be obtained using the Wald method.

Analysis will be using the ITT population as the primary analysis and PP as supportive. Progression-free survival will have sensitivity analyses performed which will be further detailed in the SAP.

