1 INTRODUCTION

This statistical analysis plan (SAP) describes the methods to be used in the analysis of study data from clinical protocol DCC-2618-03-001 (invictus) in order to answer the study objectives, and is based on Amendment 5 of the study protocol, dated 30Oct2018.

Populations for analysis, data handling rules, and statistical methods are described within this document. The statistical analyses and summary tabulations described in this SAP will provide the basis for the results sections of the clinical study report (CSR) for this trial. Pharmacokinetic (PK) analysis, pharmacodynamic (PD) and bioanalytical data analysis is not in the scope of this SAP. These analyses will be separately planned and reported. The SAP outlines any differences in data analysis methods relative to those planned in the study protocol. Any changes to the data analysis methods after the SAP is finalized will be described in the CSR.

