8.3.5 Quality of Life

Quality of life (QOL) will be based on European Organisation for Research and Treatment of Cancer Quality of Life Questionnaire for Cancer 30-item (EORTC-QLQ-C30) and the EuroQol 5-Dimension 5-Level (EQ-5D-5L) questionnaires.

The EORTC-QLQ-C30 will be summarized by scale. In all scales, a high scale score represents a higher response level. The scoring for this questionnaire will be done in 2 steps.

1. Calculate the average of the items that contribute to the scale. This will be used as the raw score for the scale, and
2. Apply a linear transformation to standardize the raw score, so that scores range from 0 to 100.

Changes from baseline to Day 1 of Cycle 2 in EORTC-QLQ-C30 Role function and Physical function will be compared between the two treatment arms using analysis of covariance (ANCOVA) model with the stratification factors as factors. If Day 1 of Cycle 2 value is missing, then the change from baseline to the end of initial study treatment will be used in the analysis.

The EQ-5D-5L is a standardized measure of health status comprised of a descriptive system including five health-related QOL states (ie, mobility, self-care, usual activities, pain/discomfort, and anxiety/depression) and a visual analogue scale (VAS) of overall health. Each dimension is rated on a 5-point response scale indicating severity of problems, where 1 is “no problems”, 2 “slight problems”, 3 “moderate problems”, 4 “severe problems”, and 5 is “extreme problems”. The five questions are scored and together contribute to the EQ-5D-5L index (utility) score between 0 and 1 (1 being perfect health), which will be calculated using the developers’ algorithm based on country-specific reference score sets (Van Hout et al., 2012). Score sets are available for Denmark, France, Germany, Japan, Netherlands, Spain, UK, US and Zimbabwe. For countries in which no score set exists (Canada, Hungary, Israel, Romania, and Sweden) the closest neighboring country will be used as a proxy (EuroQol Group, 2015), eg, UK value set for Australia, France value set for Belgium, USA value set for Canada and Singapore, and Germany value set for Poland. If scale is missing for one of the dimensions, the index (utility) score will have a missing value.

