8.5 Multiple Comparisons/Multiplicity

To control familywise type-I error, the hypothesis tests for treatment difference between DCC-2618 and placebo will be performed at two-sided 0.05 level of significance sequentially in the following order:

1. The primary endpoint PFS based on independent radiologic review
2. The key secondary endpoint ORR based on independent radiologic review
3. OS
4. QOL as determined by changes from baseline to Day 1 of Cycle 2 in EORTC-QLQ-C30 Role function and Physical function (each at 0.025 level of significance)

If any hypothesis test is not significant at $\alpha=0.05$ level, the subsequently listed analyses will be viewed as descriptive.

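### Protocol Table 18 fills a mostly blank QLQ-C30 from other patients without regard to arm, and the SAP gives a different rule without withdrawing it

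*Protocol*

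**What the plan says.** Protocol 9.4, Table 18, has one row, for the QLQ-C30, and two columns. With fewer than half the items missing the rule is "No imputation for missing". With more than half missing it is "Impute missing values by using the average score from the patients with non-missing values from within the same randomization strata". There is no column for exactly half, and the table does not say whether items are counted per scale or over the whole questionnaire.

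The randomization strata (Protocol 5.9 and 9.8.5.1) are prior lines of therapy, 3 or at least 4, and ECOG, 0 or 1–2. Arm is not a stratum. Allocation is 2:1, about 80 to 40.

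Changes from baseline to Cycle 2 Day 1 in Role and Physical function form the fourth and last step of the fixed testing sequence, after PFS, ORR and OS, at 0.025 each (Protocol 9.6, SAP 8.5).

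SAP 8.3.5 scores each scale in two steps, the first being "Calculate the average of the items that contribute to the scale", with no minimum number of answered items. It compares the arms by ANCOVA with the stratification factors. If the Cycle 2 Day 1 value is missing, the patient's own change at the end of initial treatment is used. SAP 8.4 says that missing-data handling for efficacy is in SAP 8.1 to 8.3; it carries over a version of the protocol's date table but not Table 18. SAP 1 states: "The SAP outlines any differences in data analysis methods relative to those planned in the study protocol". Neither the body of the SAP nor its summary of changes says that Table 18 has been dropped.

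**The concern.** The rule imputes where the patient has said least and does nothing where the patient has said most. The donor cell ignores arm, so a filled value carries part of the other arm's outcome and then enters the ANCOVA as if it had been observed.

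The case of exactly half missing has no rule. It arises on any scale with an even number of items. The protocol mentions "The 2 items comprising the global health status scale", so one skipped item there is enough. That scale is not a step-four endpoint, and the documents do not give the item counts for Role and Physical function.

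At stake are the size of the reported difference on the last two alpha-controlled endpoints, and the fact that two documents give a programmer different instructions for them.

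**Working it through.** **No plan figure to reproduce.** The documents give no effect size, SD, power or missing-data rate for the QLQ-C30. The 15% dropout in the sample-size section is not such a rate. The alpha split adds up: 0.025 + 0.025 = 0.05. Every missingness rate and effect size below is an assumption.

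**Expected difference under Table 18, arms pooled.** Let δ be the true difference, m_A and m_P the shares imputed on DCC-2618 and placebo, and w the DCC-2618 share of observed patients in the donor cell. Missingness is taken as unrelated to outcome within arm.

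- Donor mean = w·μ_A + (1 − w)·μ_P
- DCC-2618 mean after filling = μ_A − m_A(1 − w)δ
- Placebo mean after filling = μ_P + m_P·w·δ
- Expected difference = δ × [1 − m_A(1 − w) − m_P·w], which is δ × (1 − m) when both shares equal m

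With 80 and 40 patients:

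| Imputed, DCC-2618 / placebo | w | Factor | If δ = 10 points |
|---|---|---|---|
| 2.5% / 2.5% | 78/117 = 0.667 | 0.975 | 9.8 |
| 10% / 10% | 72/108 = 0.667 | 0.90 | 9.0 |
| 5% / 20% | 76/108 = 0.704 | 1 − 0.05×0.296 − 0.20×0.704 = 0.844 | 8.4 |
| 10% / 30% | 72/100 = 0.72 | 1 − 0.10×0.28 − 0.30×0.72 = 0.756 | 7.6 |

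In simulation (δ = 10, assumed SD 20, one stratum), the nominal 95% interval covers δ about 95%, 94%, 94% and 90–91% of the time in these four rows.

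The factor applies to a filled Cycle 2 Day 1 score or change. A filled baseline alone does not move the expected difference, because randomization gives both arms the same expected baseline. The patient's change is then still partly other patients' data.

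**Error rate and power.** Simulation with 80/40, four strata with assumed prevalences, ANCOVA on treatment and strata, two-sided 0.025, 4,000 trials per scenario, assumed effect 0.5 SD of change, equal imputed shares of 10 / 20 / 30%:

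| Method | Mean estimate | Power | Type I error |
|---|---|---|---|
| Left missing (complete cases) | 0.50 / 0.50 / 0.50 | 0.56 / 0.49 / 0.45 | 0.022 / 0.022 / 0.028 |
| Pooled donor, change imputed | 0.45 / 0.40 / 0.35 | 0.55 / 0.49 / 0.44 | 0.021 / 0.022 / 0.029 |
| Pooled donor, score imputed (assumed correlation 0.6) | 0.45 / 0.40 / 0.35 | 0.50 / 0.38 / 0.30 | 0.022 / 0.022 / 0.029 |
| Donor within arm and stratum | 0.50 / 0.50 / 0.50 | not comparable | 0.041 / 0.065 / 0.122 |

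With 10% / 30% imputed, type I error under pooling was 0.016 (change imputed) and 0.024 (score imputed). Pooling therefore biases the estimate without inflating type I error. Adding arm to the donor cell removes the bias but understates the variance, so it is not a repair.

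**Which rule acts?**

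1. The SAP's fallback starts once a Cycle 2 Day 1 value is missing. The SAP never says how many unanswered items make a scale value missing.
2. Table 18 is the only item-level rule in either document. If it is applied first, the value is no longer missing and the fallback is not reached.
3. The fallback does not cover baseline. The QLQ-C30 is first given at Cycle 1 Day 1, with no screening administration (Protocol Table 1), so a mostly blank baseline has no SAP remedy, while Table 18 would fill it.

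**The case against.** The strongest objection is that the SAP has already replaced Table 18. SAP 8.3.5 gives its own rule for exactly these endpoints, SAP 8.4 says the efficacy rules are in 8.1 to 8.3, and a table of date rules was carried over while Table 18 was not. A programmer working only from the SAP would use the patient's own end-of-treatment change. This stands in part. A reader might infer that Table 18 will govern the step-four tests and will shrink their result. The documents do not establish that. They show two unreconciled rules, one of which could be applied before the other.

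Pooling over arms is also an inference. Table 18 does not mention arm. It is the literal reading, since the strata exclude arm, and the alternative reading has the variance fault shown above.

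The size has no anchor. Questionnaires are completed on tablets at visits, and nothing in the documents suggests that 10–30% of patients would leave more than half the items blank. At 2.5% per arm the effect is negligible. This stands.

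Finally, a reader might infer a risk of a false positive QOL claim. The calculations do not support that: under pooling type I error stayed between 0.016 and 0.029 against a nominal 0.025, and the shift works against a beneficial drug.

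**Conclusion.** The concern holds in a limited form. Table 18 is a poor rule as written: it imputes only where the patient supplied least, leaves exactly half undefined and, read literally, borrows across arms. It has not been withdrawn, and the SAP leaves open when a partly answered scale counts as missing. Whether it will be used for Role and Physical function cannot be settled from the documents.

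If it is used with the arms pooled, the expected difference is multiplied by 1 − m for an equal imputed share m: 0.90 at an assumed 10%, close to 1 at 2 to 3%, and exactly 1 if nobody has more than half the items missing. Against complete cases, the power loss runs from almost none if the change is imputed to material if the score is imputed. PFS, ORR and OS are untouched, and the two QOL tests are confirmatory only if all three are significant. The correction is worth making because it is cheap and removes an ambiguity from an alpha-controlled endpoint.

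**What to change.** - Withdraw Table 18 and record this in the SAP as a difference from the protocol. The adverse-event sentence in Protocol 9.4 that points to Table 18 for missing dates should then point to the date table, Table 17.
- Add to SAP 8.3.5: a scale is scored as the mean of its answered items if at least half of that scale's items are answered; otherwise it is set to missing at that visit. This covers exactly half and makes the count per scale.
- State that the existing end-of-treatment rule then applies to a scale missing at Cycle 2 Day 1, that a missing baseline scale is not filled from other patients, and that other patients' averages are never used, whether pooled or within arm.

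The cost is one protocol table and a few SAP sentences. The downside is that a few scale scores become missing instead of being filled in.
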